## Study Protocol

### Summary of Project

**Background:** It is currently estimated that between 50-60% of individuals with an alcohol use disorder also suffer from comorbid anxiety and/or depression (Swendsen & Marikangas, 2000). This statistic makes alcohol dependence and emotional disorders the highest co-occurring disorders among general populations (Conway, Compton, Stinson, & Grant, 2006). Individuals who suffer from both disorders often experience poor overall health, physical injury, marital dysfunction, increased suicidality, early mortality (Beidel, Frueh, & Hersen, 2014). Given the increased consequences for adults suffering from both disorders, there is a critical need for research aimed at designing effective treatments for alcohol misuse and co-occurring emotional problems.

Individuals with alcohol problems who also suffer from an emotional disorder (compared to those who do not) experience high rates of relapse, have greater functional impairment, and have poorer responses to treatment among individuals with significant alcohol problems. Existing treatments for alcohol misuse and co-occurring anxiety/depression typically include parallel or sequential interventions, meaning that individuals are treated for one disorder followed by the other, or separate treatments are conducting at similar times by two different professionals (DeVido & Weiss, 2012; Mueser, Noordsy, Drake, & Fox, 2003). However, neither approach takes into consideration the interconnectedness of these highly comorbid disorders, and often times there is little communication between professionals when the disorders are treated separately. For example, a person who suffers from depression would find it difficult to quit drinking if their depressive symptoms (i.e., triggers for drinking) were not addressed in treatment. In turn, this same person's depressive symptoms would likely be made worse by repeated unsuccessful attempts to control their drinking. In this case, it would be challenging for the individual to make progress for either disorder/in either treatment. Therefore, treatments that do not target the symptoms of both alcohol use and anxiety/depression *simultaneously* may not be sufficient. There are limited integrated treatments designed to target alcohol use and emotional problems simultaneously.

**Goal:** Considering the limitations of current interventions for comorbid alcohol misuse and anxiety and/or depression, and the staggering rates of these co-occurring disorders, there is a need for integrated treatments designed to target both disorders simultaneously. Furthermore, it is important that said integrated treatment options are both cost-effective and feasible, thus reducing the burden on the health care system. Therefore, an *online* integrated treatment stands to provide both an effective and economical option. There is a growing body of literature suggesting the potential effectiveness of combining Cognitive Behavioural Therapy (CBT) and Motivational Interviewing (MI) to treat alcohol misuse and comorbid emotional problems (Riper et al., 2014). These treatments teach people coping skills for both disorders (e.g., challenging negative thoughts), while simultaneously improving their motivations to change problem behaviours (Hofman, 2012; Lundahl & Burke, 2009). To date, the only intervention of this nature has been developed at the Swiss Research Institute for Public Health and Addiction in German (Schaub et al., 2016). This study will adapt this intervention for use in English speaking young adults in Canada. By developing an online integrated treatment for alcohol use and emotional problems, we will be able to reach rural and Northern communities where the prevalence rates of these disorders are particularly high. Furthermore, online treatments are

associated with less stigma and shame, which may provide additional opportunities for early intervention through participation in the intervention. Overall, this accessible and cost-effective treatment stands to reduce the symptoms of both alcohol misuse and anxiety/depression, thus potentially improving the overall health and well-being of hundreds of Canadians.

## **Method**

The study design will be a two-arm randomized controlled trial (RCT). This method is considered the “gold standard” in conducting clinical research in order to determine the effectiveness of an intervention. Prior to initiating the full study, a pilot-testing phase will be used to ensure that the intervention components are translated, created, and presented in ways that are most helpful and engaging for young adults. This will also be done in order to receive feedback on the modules prior to opening them up to the public. In order to obtain this pilot feedback, the full intervention will be provided to both knowledge users and professionals. Once we have received feedback, we will meet as a team (i.e., primary investigators, graduate students, research assistants), to discuss changes and apply feedback as necessary.

After completion of the pilot phase, we will begin the active study phase. First, interested participants will be encouraged to contact the lab via e-mail. Once they have expressed an interest in the study, they will be given access to information about the study and the consent form. After reading the informed consent form, they will be able to provide informed consent on the study website and then register for an account. Once they have consented to participate and registered, they will visit their e-mail inbox to verify their e-mail address and create a password. Once they have confirmed their login information, they will immediately be directed to the baseline assessment measures. These measures will also be used to determine whether participants are eligible to participate. If at any point a participant is deemed ineligible on a measure, they will automatically be redirected to a “Thank You” page so as not to make them fill out questionnaires unnecessarily. In order to determine eligibility, participants will first be assessed for suicidality. Individuals who are deemed “Minimal” or “Lower” risk on the screener will be able to proceed to the remainder of the questionnaires in order to determine eligibility. Those that are identified as “Higher” risk will immediately be deemed ineligible. At this time, they will be directed to a screen with urgent information on how to proceed next. This page will provide them a list of resources in their area that we will urge them to contact as soon as possible. We will make it clear that their safety and well-being is our utmost concern by stating that we are concerned about their safety and strongly encourage them to access supports as soon as they can.

If individuals meet the eligibility criteria in terms of suicidality (i.e., minimal or low risk), they will then be provided with the remainder of the baseline measures. If participants do not meet our eligibility criteria, we will still provide them with access to the intervention, but will not track their data, and their responses to the baseline measures will not be retained. After eligible participants complete the baseline measures, they will be randomly assigned to one of the two treatment conditions using a 1:1 ratio. The first condition will be the integrated treatment (i.e., active experimental condition) where participants will have access to the 12 treatment modules, developed using combined elements of CBT and MI. Throughout the modules, participants will identify goals related to alcohol use and mood, learn strategies to cope with alcohol cravings, triggers, and social pressures, and learn how to prevent relapse. Modules will also include

content designed to target anxiety and depression, focusing on strategies designed to help reduce negative thinking and worry, increase behavioural activation, and increase self-care (e.g., relaxation techniques, sleep hygiene).

Participants will have 8-weeks to complete the modules and will immediately be given access to all modules. While it is technically possible to work through the modules in any order, they will be encouraged to work through the modules sequentially. In order to bring a small social presence to the treatment, each module will begin with a brief introduction video. Previous research suggests that adding this social factor will personalize the online program and may influence accountability (Mohr, Cuijpers, & Lehman, 2011), especially considering that it is self-guided. The purpose of these videos will be to summarize the content of the upcoming module, as well as provide motivation to continue with the program. Participants will also be supported by an e-coach during active treatment. This coaching content will all be automated, with the exception of specific questions participants may have for their e-coach. They will be able to ask these questions over e-mail. The purpose of the e-coach will be to answer any questions the participant may have as they work their way through the modules. Coaches will provide ongoing feedback about module progress and provide reminders about completing each section of the intervention. They will also provide support to participants should have they additional questions or concerns throughout the program. Therefore, the use of e-coaches will help to reduce the risk of attrition. Research shows that both automatic and personal feedback are central to improving adherence during self-guided behaviour change interventions (Mohr et al., 2011). At the outset of treatment, participants will also be asked to select an animated personal companion whom they identify with in terms of sex, age, occupation, and family background. The purpose of this companion is to provide advice and examples pertaining to the content throughout the intervention. The personal companion will appear in each module at least once.

The second condition will be psychoeducational (i.e., the control condition). Participants randomly assigned to the control condition will receive links to websites that provide general psychoeducation about alcohol (e.g., <https://www.niaaa.nih.gov/publications/brochures-and-fact-sheets>), and mental illness (e.g., <https://www.jack.org/resources>). Therefore, the control group will have access to available online psychoeducational material. A psychoeducation control group is common in clinical research in order to determine the efficacy and effectiveness of online interventions (Schaub et al., 2016). It is also important as we do not want to harm patients in any way or prevent them from getting something that is already established are effective. For ethical reasons, participants in the psychoeducation control group will be given access to the active integrated treatment at the end of the study, regardless of whether they have completed all of the assessments.

*Research Instruments:* Participants will be assessed at three time points throughout the study: at baseline (i.e., prior to treatment; T0), immediately following the 8-week treatment (T1), and at follow-up (i.e., 24 weeks, T2). The primary outcome of interest will be the number of standard drinks consumed during the seven days prior to the assessment. This will be assessed using the Timeline Follow-Back (TLFB; Sobell & Sobell, 1992) procedure at all assessment points (T0-T2). The TLFB has been widely used in studies, including treatment studies (Keough, O'Connor, & Colder, 2016; Schaub et al., 2016). As a secondary outcome, depressive symptoms will also be assessed at all time points using the CES-D, a 20-item self-report questionnaire used to indicate

depression severity (Radloff, 1977). Anxiety symptoms will also be assessed at all three assessment points using the GAD-7, a 7-item self-report questionnaire used to measure the severity of anxiety symptoms (Spitzer, Kroenke, Williams, & Löwe, 2006). In order to determine clinically significant and combined reduction in alcohol use and comorbid emotional problems, we will use a combined outcome of alcohol use on the AUDIT, and cut-offs from the GAD-7 and CES-D. We will also measure participants' quality of life using the World Health Organization Quality of Life assessment (WHOQOL-BREF). This is a 26-item self-report measure that assesses functionality in various life domains (The WHOQOL Group, 1998). A sum score will be used to assess overall quality of life at all assessments points (i.e., T0-T2). We will also collect information on participants' use of other substances using the National Institute on Drug Use (NIDA ASSIST; National Institute on Drug Abuse, 2009), and their executive functioning using the WebEx (Buchanan et al., 2010). This information will be collected to examine transfer effects to other substances, as well as to examine the potentially moderating effects of executive functioning. Finally, we will obtain a measure of participants' level of motivation in terms of importance, confidence, and readiness. Participants will complete all measures at each of the three time points, with the exception of the Demographics questionnaire and the AUDIT, which will only be completed at baseline.

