## **Participants**

A target sample of 400 participants will be recruited for the study. Participants will include Canadian young adults struggling with moderate alcohol misuse and emotional problems. Inclusion criteria will include: 1) individuals between 18 and 35 years old, 2) reporting difficulties with alcohol indicated by a score  $>3$  for women and  $>4$  for men on a brief version of the Alcohol Use Disorders Identification Test [AUDIT; Saunders et al., 1993] known as the AUDIT-C, 3) reporting depression and/or anxiety symptoms indicated by a score  $>16$  on the Center for Epidemiological Studies Depression Scale [CES-D] and/or a score of  $>5$  on the Generalized Anxiety Disorder Scale-7 [GAD-7], 4) fluency in English, and 5) have weekly Internet access. Exclusion criteria will include the following: 1) self-reported engagement in other psychological or pharmacological treatments for alcohol misuse and/or depression/anxiety; 2) elevated suicidality (defined as scoring greater than "minimal risk" on a screener); and 3) current psychosis or mania. Interested participants will be invited to contact the primary investigators for a link to the study website. Participants will be sent a link with information about the study and be able to provide informed consent electronically directly on the treatment website. They will also be provided with detailed instructions on how to create a user account for the self-help program, and be encouraged to contact the researchers should they have any trouble at this stage. After they have provided informed consent, they will be able to register on the study website. They will need to create a username as well as verify their account via e-mail before they can access the website. After informed consent has been obtained and their account has been verified, they will immediately be asked to complete the baseline assessment measures. If they are eligible, they will be able to access the 12 treatment modules and continue with the study procedure. Interested adults with clinically-elevated symptoms (i.e., those who score above the cut-offs on our screening tools) will be still given access to the integrated intervention, and will be given the contact information for a mental health professional in their area. However, they will be excluded from the study and their data will not be tracked.

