### **Anonymity and Confidentiality**

In order to determine who is eligible to participate in the study, potential participants will need to create a unique username to access the program. Outside of this username, no identifying information will be collected on the study website. Therefore, the only potentially identifying information collected would be if participants create a username using their first and last name. Eligible participants will also be given a unique participant ID. Participant ID numbers will be automatically generated by the study website immediately after registration using an incremental number system. The data collection file will contain these participants ID's and scores on each measure, but will not contain identifiable information (i.e., usernames). The data file used for statistical purposes will remain completely anonymous at all times. The de-identified raw data will be retained indefinitely for dissemination purposes/meta-analyses in order to inform future research. While we will be using e-mail addresses to contact interested participants this information will never be recorded nor linked to their data. All study data will be automatically collected on the website without identifying information.

Since we will not be collecting identifying information, no formal records of client data will be retained. The only data retained will be the scores to questionnaires obtained through the study

website itself. Furthermore, while the program was designed using in-person treatment methods, it is ultimately a self-help program. Therefore, it is not necessary nor feasible to make a client record for each participant given the nature of the self-guided program as well as the lack of identifying information being obtained.

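### The plan neither excludes nor records earlier or outside use of the programme, although people who fail screening are given access to it

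*Protocol*

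**What the plan says.** The protocol describes what ineligible people receive in three places.

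- **Method, paragraph on randomisation.** The statement is general: "If participants do not meet our eligibility criteria, we will still provide them with access to the intervention, but will not track their data". The same sentence adds that "their responses to the baseline measures will not be retained".
- **Participants.** Access is stated for a narrower group, adults whose symptoms are above the screening cut-offs. They "will be still given access to the integrated intervention, and will be given the contact information for a mental health professional in their area", and they are left out of the study and not tracked.
- **Method, paragraph on the start of the active phase.** "If at any point a participant is deemed ineligible on a measure, they will automatically be redirected to a" thank-you page, and people at higher suicide risk are sent to a page of resources. Access to the modules is mentioned for neither group.

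On previous exposure, Participants lists three exclusions. The nearest is "self-reported engagement in other psychological or pharmacological treatments for alcohol misuse and/or depression/anxiety"; the others are elevated suicidality and current psychosis or mania. In the pilot, "In order to obtain this pilot feedback, the full intervention will be provided to both knowledge users and professionals".

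On the control arm, "Participants randomly assigned to the control condition will receive links to websites that provide general psychoeducation about alcohol" and mental illness. Controls are offered the active programme only at the end of the study.

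On identity, Anonymity and Confidentiality says the study website holds no identifier beyond a username. Of e-mail addresses it says "this information will never be recorded nor linked to their data".

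**The concern.** The trial compares people who have the modules with people who do not. The protocol opens a second way to the modules, outside randomisation, and has no means of seeing whether anyone in the trial has used it.

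Two kinds of exposure would matter. First, someone who failed screening and used the modules could later qualify, for example once outside treatment has ended, and be randomised. That person brings part of the treatment effect into the baseline and has less left to gain in the active arm. Second, a control could obtain the modules during the 24 weeks of follow-up. Both shrink the arm difference. The SAP plans for a small effect (g = .25) and makes no allowance for dilution, so a null result could not be told apart from a diluted one.

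**Working it through.** **1. Do the documents close either route?**

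| Possible safeguard | What the documents contain |
|---|---|
| Exclusion for earlier use | None. The first exclusion concerns other treatments, and a person who has finished these modules is not clearly engaged in one. |
| Matching a new registration to an old one | Not possible from the study data: screening answers of ineligible people are discarded, the site holds only a username, and e-mail addresses are not linked to data. |
| E-mail verification at registration | Shows that the applicant controls an address, not that the person is new. |
| Duplicate-registration check | None described. |
| Measure of module use in controls | None among the listed measures (TLFB, CES-D, GAD-7, AUDIT, WHOQOL-BREF, NIDA ASSIST, WebEx, motivation, demographics). |
| Analysis for contamination | None. The SAP's one sensitivity analysis is prompted by attrition. |

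Both routes are therefore open and unrecorded. Nothing in the documents says how often either would be taken.

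**2. Reproduce the planned sample size.** Inputs from the SAP: g = .25, power .80, α = .05, sidedness not stated. From the protocol: 1:1 allocation. For a two-sample t-test with n per arm, the noncentrality is g × √(n/2).

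- One-sided .05, n = 199: .25 × √99.5 = 2.494 on 396 df, power .801. With n = 198 power is .799, so the smallest total is 398, which matches the SAP.
- Two-sided .05: the smallest total is 506, and 199 per arm gives power .701.

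The stated N is reproduced only with a one-sided test, so that is the reference setting below.

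**3. Illustrate the dilution.** Let c be the share of controls who gain the full active effect. The expected difference becomes g × (1 − c), and the N needed for the same power grows by 1/(1 − c)². Every value of c is an assumption.

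| c | Controls out of 199 | g × (1 − c) | Power, one-sided | Power, two-sided | N multiplier |
|---|---|---|---|---|---|
| 0 | 0 | .25 | .801 | .701 | 1.00 |
| 5% | about 10 | .2375 | .764 | .657 | 1.11 |
| 10% | about 20 | .225 | .724 | .610 | 1.23 |
| 20% | about 40 | .20 | .636 | .512 | 1.56 |

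Full benefit is the upper limit. If exposed controls gain half the effect, c counts half: 10% exposed then gives the 5% row, and 20% exposed gives the 10% row.

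**4. Previously exposed people who are randomised.** Allocation is 1:1, so they fall evenly across arms in expectation. The result is a smaller contrast among them, not an imbalance between arms. The documents give no basis for putting a number on it, and the table does not cover it.

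**The case against.** The best defence is that access for excluded people is a deliberate and reasonable choice, and that serious contamination needs a chain of unlikely steps. A control would have to know that failing the screen opens the modules, write to the lab again, consent again, verify another account and answer falsely, although the programme is already promised at the end of the study. Twenty per cent would mean about 40 of 199 controls doing this. That stands: the route is possible but not shown, and the larger shares in the table should not be read as forecasts.

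Four stronger readings are tempting, and the documents do not support them:

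- **Everyone who fails screening receives the full programme.** Only the general sentence in Method says so. The thank-you and resource pages, and the narrower group in Participants, leave this unsettled.
- **Ineligible people get the modules at the moment of screening.** No timing, mechanism or site is given; access might be arranged by staff or on a separate page.
- **Pilot users will enter the trial.** Nothing is said about their number, age or symptoms, so this route is weak.
- **Exposure could never be detected.** The automated feedback on module progress suggests that the site holds some usage information by account, and lab staff might notice a repeat request. But no check is written, and data on open-access users are not to be tracked.

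It is also fair that the remedies rely on self-report and would miss someone determined to conceal use. They would still catch honest previous users and honest controls, which the present plan does not.

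**Conclusion.** The gap is real, but its size is unknown. As written, a previous user of the programme can be randomised, and a control's use of the modules would go unrecorded. Any such exposure dilutes the contrast toward no effect. The fall in power from .80 to .76, .72 or .64 rests on assumed shares of 5, 10 and 20%, full benefit in every exposed control, 199 analysed per arm and a one-sided .05 test. At the low end the loss is modest. The documents do not establish that contamination will occur, so this is a low-cost improvement and not evidence that the comparison is invalid. The case for acting is that nothing in the plan would otherwise show whether dilution had happened.

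**What to change.** 1. **Reconcile the text.** Make the two Method paragraphs and the Participants section agree on which ineligible people receive access, and how. Ineligible applicants keep whatever access the reconciled text gives them.
2. **Screen for earlier use.** Add an exclusion, asked as one item at screening, for previous access to this programme (pilot or open access) or an earlier registration in the trial.
3. **Measure exposure in controls.** Add one item at T1 and T2 asking controls whether they have used any of the modules. Report the proportion beside the primary result. Add to the SAP a sensitivity analysis that takes account of reported exposure, keeping the comparison of all participants as randomised as the primary analysis.
4. **Optional.** Issue open access through a link separate from trial registration. This is a partial safeguard, since it does not stop someone who writes from a second address.

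The cost is one exclusion line, one screening item, one follow-up item and a sentence in the SAP. A few previous users are lost to recruitment, and the items depend on honest answers. No further identifying data need be stored, so the protocol's confidentiality commitments are unaffected.

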### **Risks and Benefits**

*Possible Risks:* There are increased risks associated with recruiting young adults with alcohol misuse and emotional symptoms. We would expect higher base rates of suicidal ideation and self-harming behaviours in these individuals relative to those without these mental health

concerns. Therefore, we will have safeguards in place in order to minimize the risk of harm. Young adults who report significant suicide ideation and/or plans during screening will be given a recommendation to visit their local medical professional (GP or hospital) for support as soon as possible. We will also be monitoring changes in suicidality at three time points, and will direct participants to emergency services if needed. Supports will also be accessible to participants at all times via the menu item “Help Me” on the intervention website. This will include a list of mental health services, including community resources, public and private psychologists, hospitals, and helplines. Participants in the control condition (psychoeducational) will be given access to the active treatment after the final assessment (6-months). They will receive all elements of the integrated intervention. While there is a risk that the content may be potentially distressing to some participants, resources will be provided as safeguards in order to mitigate these feelings of distress.

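### The protocol does not reconcile what applicants excluded for 'Higher' suicidality or psychosis/mania receive: read literally they may get the modules untracked, and no record of exclusions by reason is planned

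*Protocol*

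**What the plan says.** Several parts of the protocol describe what happens to someone who is screened out.

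- **Method, general exit.** Anyone found ineligible on a measure is stopped early: "they will automatically be redirected to a “Thank You” page". The stated purpose is to spare them unnecessary questionnaires.
- **Method, 'Higher' suicide risk.** "Those that are identified as “Higher” risk will immediately be deemed ineligible. At this time, they will be directed to a screen with urgent information". That screen lists local resources and urges the person to contact them. Module access is not mentioned.
- **Method, after the suicidality step.** The sentence on passing the suicidality screen is followed directly by: "If participants do not meet our eligibility criteria, we will still provide them with access to the intervention, but will not track their data". Baseline responses of these people are not retained.
- **Participants.** The exclusions include elevated suicidality and "current psychosis or mania". The section says eligible people can go on to the 12 modules. It then says that adults above the cut-offs on the screening tools still get the intervention and a local professional's contact details, but are excluded and untracked.
- **Informed Consent.** Those found eligible after the baseline measures are given access.
- **Risks and Benefits.** "We will also be monitoring changes in suicidality at three time points, and will direct participants to emergency services if needed". The section also recommends a GP or hospital visit for significant ideation or plans, and describes the 'Help Me' menu.

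**The concern.** The access sentence in Method is general. It carves out neither the group excluded for 'Higher' suicidality nor the group with current psychosis or mania. Someone building the website from this text would not know whether these applicants are shown a closing page, a crisis page, the modules, or some sequence of these.

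Two things are at stake. The first is consistency of safety handling: the repeat suicidality checks in Risks and Benefits belong to the study assessments, and a person whose data are not tracked would not receive them. The second is reporting: baseline answers of ineligible people are discarded and no screening log is described. The plan therefore does not provide for counting exclusions by reason, or for checking afterwards which route a 'Higher'-risk applicant was given.

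**Working it through.** No sample size, power or rate enters this point. The check sets the statements side by side and then counts planned suicidality checks.

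**1. Which statements cover a 'Higher'-risk applicant?**
- This person is ineligible (Method), so the general 'Thank You' exit applies on its wording.
- The urgent-information screen applies specifically.
- The access sentence applies too, since it covers anyone not meeting the criteria.
- The sentences in Participants and Informed Consent that link access to eligibility do not include this person.

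That makes three exit descriptions (closing page, urgent screen, untracked access) and no sentence that orders or limits them.

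**2. Which statements cover an applicant with psychosis or mania?** Participants lists the exclusion, but the protocol names no screening instrument and no dedicated exit. Only the general wording governs: the 'Thank You' page and the access sentence.

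**3. Whom does the above-cut-off sentence in Participants describe?** Inclusion requires an AUDIT-C score above 3 (women) or above 4 (men), together with CES-D above 16 and/or GAD-7 above 5. Scoring above those cut-offs is therefore a condition of entry. No upper limit on these scales is listed as an exclusion. Among the screeners the protocol names, only the suicidality screener excludes for a high score. Unless an unstated upper cut-off is intended, the sentence either contradicts the inclusion criteria or refers to the suicidality-excluded group.

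**4. Planned suicidality checks.** Inputs: three time points (Risks and Benefits), taken to be T0, T1 (8 weeks) and T2 (24 weeks) from the Research Instruments paragraph.
- Enrolled participant: 3 in total, 3 − 1 = 2 after baseline.
- 'Higher'-risk applicant given untracked access: 1 (the screen itself, response not retained), 1 − 1 = 0 afterwards.

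**5. What other safeguards remain?** The urgent resource page, the GP/hospital advice, a professional's contact details (for those above cut-offs) and the 'Help Me' menu. Each is given once or waits for the user to seek it. None is a repeat check.

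**6. What record remains?** Method discards the baseline responses of ineligible people. Anonymity and Confidentiality describes incremental ID numbers generated on registration, which precedes screening, but also speaks of IDs for eligible participants. A total of registrations might be recoverable. Nothing described would give the criterion failed, the page shown or whether access was granted.

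**The case against.** The best case for the protocol has five parts.

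- **The routes may be sequential.** A general exit rule followed by a specific one is ordinary drafting, and being shown a page does not preclude later access. The sentences on eligible people getting access do not say that only they do. This stands: the statements are unreconciled rather than strictly exclusive. But the sequence is never stated, and it would leave the difference in later checks as it is.
- **The access sentence may cover only people who passed the suicidality screen and failed something else.** Its position allows that reading. Its wording does not limit it so, and the above-cut-off sentence in Participants points the other way.
- **Safeguards exist.** They do, and they must be acknowledged. The sentence beginning "While there is a risk that the content may be potentially distressing to some participants" goes on to name resources as the mitigation, so a reader should not infer that three-point monitoring was offered as the safeguard against distressing content. The documents offer that monitoring for suicidality.
- **Excluded people are not trial participants.** Absence of trial follow-up does follow from exclusion. The protocol nonetheless undertakes to give them the intervention, so it should say on what terms.
- **Non-retention of responses is not the same as keeping no count.** This also stands. A reader might infer that the number of 'Higher'-risk applicants could never be known, or that the population to which the result applies could not be described. The documents support neither: they say only that responses are not kept, and the eligibility criteria and baseline data of those randomised describe the study population.

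**Conclusion.** The point holds as an unreconciled set of instructions and a missing provision for recording exclusions. On the literal text, an applicant excluded for 'Higher' suicidality could be given the modules with 0 later suicidality checks, against 2 for an enrolled participant. An applicant with psychosis or mania falls under the same general wording with no specific route. Exclusions by reason, and the route actually followed, are not provided for in the record.

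This assumes that the three monitoring time points are T0, T1 and T2, and that untracked users do not complete the T1 and T2 measures. How many people would be affected cannot be estimated from the documents.

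A reader might go further and infer that the sponsor means to give its highest-risk applicants unmonitored treatment, or that psychosis and mania were excluded on grounds of risk. The protocol states no such intention and gives no reason for that exclusion. Nor can it be said that applicants are not told about the lack of monitoring: Informed Consent says safety arrangements are covered, and the consent form is not in the reviewed copy.

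This should be fixed, but it does not touch the randomised comparison. Sample size and primary analysis are unaffected.

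**What to change.** 1. Reconcile the Method, Participants and Informed Consent sections into one statement or table, by reason for ineligibility ('Higher' suicidality, psychosis/mania, other treatment, below symptom cut-offs, age or language, no weekly Internet access). For each reason, state which page is shown and whether module access is given. Which groups have access is the sponsor's clinical decision.
2. In the same revision, correct the above-cut-off sentence in Participants against the inclusion criteria. Settle also whether 'Lower' suicide risk is eligible: Method lets such applicants proceed, while Participants excludes anyone above minimal risk.
3. State plainly whether the suicidality monitoring in Risks and Benefits applies to excluded users who have access.
4. Replace the blanket non-retention rule with an anonymous screening log: date, criterion failed, page shown, access yes or no, with no scores or identifiers. This allows exclusions to be reported by reason and the route to be checked.

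The cost is protocol and consent wording and an automatic log on the existing website. The small downside is that a minimal non-identifying record is kept for ineligible people, which the consent form should mention.
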